6 CLINICAL AND LABORATORY EVALUATIONS/STUDY PROCEDURES

6.1 Schedule of Activities

Evaluation	Screening (-90 days)	Day 1	2 wks	3 wks	4 wks	5 wks	6 wks	9 wks	12 wks
Written Informed Consent	X								
Inclusion/Exclusion Review	X	X							
Documentation of Disease/Disorder	X	X							
Hoehn & Yahr	X	X	X				X		X
Medical History • Overall Medical History • Medical History of PD	X	X					X		X
Concomitant medication review	X	X	X				X		X
Orthostatics^a	X	X	X				X		X
MDS-UPDRS Motor assessment^b	X	X	X				X		X
Physical examination	X	X					X		X
Randomization^c		X							
Dispense Study Drug^d		X							
Blood Draw		X ^c					X		X
MRI		X ^c							X
Neurological examination	X	X					X		X
Body weight and height	X	X	X				X		X
Vital signs	X	X	X				X		X

Finger Tapping Assessments		X	X				X		X
Behavioral Assessments									

 Columbia Suicide Severity Rating Scale Questionnaire for Compulsive Disorders (C-SSRS) Beck Anxiety Inventory Beck Depression Inventory Parkinson's Disease Questionnaire (PDQ-39) 	X ^e	X	X ^f				X		X
Sleep assessment		X					X		X

 Pittsburgh Sleep Quality Index 									
Recent Falls			X	X	X	X	X	X	X
Cognitive Assessments		X					X		X

 Hopkins Verbal Learning Test (HVLT) Symbol Digit Modalities Test (SDMT) MoCa 									
Auditory/Speech Assessment		X	X				X		X
Pregnancy Test for Women of Child-Bearing potential	X	X	X				X		
Timed Up and Go Assessment		X	X				X		X
Drug Accountability/ Compliance			X	X	X	X	X	X	X
Adverse Event Review			X	X	X	X	X	X	X

a) Participants will lie in the supine position for 5 minutes and have their blood pressure checked. The patient will then sit up for 1 minute and have their blood pressure re-checked. The patient will then stand for 3 minutes and have their blood pressure checked. If the participant has a decrease in the systolic blood pressure by 20 or more mmHg after standing for 3 minutes, or a decline of 10 or more mmHg in the diastolic blood pressure, they will be considered to have orthostatic hypotension.

- b) All MDS-UPDRS Motor Assessments will be collected when the participant is in the practically defined OFF state, meaning they have not taken their dopaminergic PD medications for > 6 hours at the time of assessment; this assessment will be video recorded to ensure rater reliability
- c) Baseline assessments on day 1 will occur PRIOR to randomization or the study drug being dispensed after the site coordinator has determine the subject is still eligible for participation.
- d) This will be performed twice at the baseline visit: prior to administration of TZ and 3 hours after administration of TZ
- e) Only the Beck Depression, Beck Anxiety, and C-SSRS will be assessed at the screening visit, per exclusion criteria
- f) At the Week 2 visit only the PDQ-39 will be assessed.

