4 SELECTION AND ENROLLMENT OF SUBJECTS

4.1 Inclusion Criteria

1. Men or women aged 40 and older with the diagnosis of idiopathic PD per UK Brain Bank criteria
2. Hoehn-Yahr Stage I-III, on stable dopaminergic treatment regimen for \geq 4 weeks prior to baseline.

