6.3.5 Treatment History

Participants will be asked to provide a full history of any medications, over-the-counter products, herbal supplements, nutraceuticals, or devices that have been used for the treatment of PD or PD-related symptoms. They will also be asked to recollect (to the best of their knowledge) the timing of these treatments (i.e. when did they start the medication, when were dosage adjustments made, when was the treatment stopped). For medications that were used specifically for the treatment or relief of symptoms of PD, participants will be asked what the reason for discontinuation was, if applicable. Participants will also be asked to provide information about dosages, dosage form (capsule, tablet, etc) route of administration, dosing schedule (Appendix C)

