6.3.8 Clinical Assessments

- Hoehn & Yahr
 - Collected to measure disease severity as well as progression throughout study
- Orthostatics
 - Collected to measure if participants are having worsening orthostatic hypotension.
 - If orthostatic hypotension is present, this assessment will NOT be able to determine if it is secondary to the study medication or autonomic failure that occurs in PD.
- Physical examination
 - This will be a simple physical exam to measure the general health of the participant independent of their PD
- MDS UPDRS Part 3
 - This portion of the MDS-UPDRS specifically measures motor function. This will only be collected when subjects are in the practically defined "off-period" meaning that they have not taken their PD medications within 6 hours of the assessment
- MDS-UPDRS Part 4
 - This portion of the MDS-UPDRS will use historical and objective information to assess the motor complications of dyskinesia and motor fluctuations including off-state dystonias
- Vital signs/Height & Weight

FAST TZ-PD

Version 2.0

Version date: 11/12/2019

- Participants will have their heart rate, respiratory rate, blood pressure, and core body temperatures measured as well as their height and weight
- Neurological Exam

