9.1.3 Exploratory Outcome(s)

- Difference in ATP levels in red blood cells and brain within subjects before and after taking study drug on day 1
- Difference in ATP levels in red blood cells and brain within subjects at 6 and 12 weeks compared to baseline reading
- Difference in ATP levels in red blood cells and brain between groups at 6 weeks and 12 weeks
- Slope of change over 12 weeks of the MDS-UPDRS Part 1
- Slope of change over 12 weeks of the MDS-UPDRS Part 2
- Slope of change over 12 weeks of the MDS-UPDRS Part 3 (OFF)
- Slope of change over 12 weeks of the MDS-UPDRS Part 4 (OFF)
- Absolute change over 12 weeks of the MDS-UPDRS Parts 1, 2, 3, 4, and TMS (OFF)

FAST TZ-PD

Version 2.0

Version date: 11/12/2019

- Slope of change over 12 weeks of MDS-UPDRS TMS (OFF) (direct comparison for efficacy)
- Slope of change over 12 weeks of the Hoehn & Yahr Score
- Slope of change over 12 weeks of all cognitive assessments between placebo and active group
- Slope of change over 12 weeks of sleep assessments between placebo and active group
- Slope of change over 12 weeks of behavioral assessments between placebo and active group

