Amantadine	Cabergoline	L-Dopa Slow Release	Memantine	Rasagiline	Selegiline patch
Apomorphine	Entacapone	L-Dopa Soluble	Pergolide	Ropinirole	Selegiline sublingual
Bromocriptine	L-Dopa Dual Release	L-Dopa Standard	Piribedil	Rotigotine	Tolcapone

Parkinson's Disease Medication Log.

Medication Log Table

Line #	Medication Class	Medication Name (Trade or generic name)	Maximum Dose (Specify units)	Estimated Total Duration of Exposure (Check units)	Medication Use Ongoing?	If Applicable, Reason for Discontinuation
Data to be filled out by site	Data to be filled out by site	Data to be filled out by site	Data to be filled out by site	 Years  Months  Weeks  Days	 Yes  No  Unknown	 Lack of efficacy  *Side Effect:  Other:
Data to be filled out by site	Data to be filled out by site	Data to be filled out by site	Data to be filled out by site	 Years  Months  Weeks  Days	 Yes  No  Unknown	 Lack of efficacy  *Side Effect:  Other:
Data to be filled out by site	Data to be filled out by site	Data to be filled out by site	Data to be filled out by site	 Years  Months  Weeks  Days	 Yes  No  Unknown	 Lack of efficacy  ¹ Side Effect:  Other:
Data to be filled out by site	Data to be filled out by site	Data to be filled out by site	Data to be filled out by site	 Years  Months  Weeks  Days	 Yes  No  Unknown	 Lack of efficacy  ² Side Effect:  Other:

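### The OFF motor exam has only a 6-hour minimum since the last PD dose, worded two ways, and the plan neither holds that interval constant across visits nor records it

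*Combined protocol and SAP*

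**What the plan says.** Two places define the OFF state for the motor exam.

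- Section 6.1, footnote b: "in the practically defined OFF state, meaning they have not taken their dopaminergic PD medications for > 6 hours".
- Section 6.3.8, under MDS-UPDRS Part 3: "meaning that they have not taken their PD medications within 6 hours of the assessment".

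The exam is scheduled at screening, Day 1 and weeks 2, 6 and 12. Footnote b adds one quality control: "this assessment will be video recorded to ensure rater reliability".

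Section 9.1.3 lists "Slope of change over 12 weeks of the MDS-UPDRS Part 3 (OFF") among the exploratory outcomes, with the absolute 12-week change and the TMS (OFF) slope. Of these, only the TMS slope is marked as the direct efficacy comparison. Section 9.4 assigns linear mixed models to the slopes and independent t-tests to the absolute change. It names no covariate for time since the last PD dose.

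On background treatment, section 4.1 requires participants to be "on stable dopaminergic treatment regimen for" at least 4 weeks before baseline, with no limit by formulation. Section 6.3.5 collects dosage, "dosage form (capsule, tablet, etc) route of administration, dosing schedule (Appendix C"). The drug-name table in Appendix C includes "L-Dopa Slow Release" and "Selegiline patch".

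**The concern.** A minimum interval allows one participant to be examined a little over 6 hours after a dose at one visit and many hours later at another. If any PD-drug effect remains at 6 hours and fades afterwards, the Part 3 score moves with the interval even when the disease has not changed. That movement enters every slope and change score.

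The two definitions also differ on what is withheld. The class table in Appendix C lists anticholinergics and antiglutamate agents alongside levodopa and dopamine agonists, so staff following footnote b and staff following 6.3.8 could prepare the same participant differently. Both passages speak of medication not having been taken, and neither says how that applies to a patch being worn or to a slow-release product.

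At stake are the precision of the exploratory motor outcomes, which the synopsis says will guide later trials, and the ability to defend the OFF label afterwards. A dose time not noted at the visit cannot reliably be reconstructed later.

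**Working it through.** **Step 1: the text.**

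| Question | 6.1, footnote b | 6.3.8 | Elsewhere |
|---|---|---|---|
| Minimum interval | more than 6 h | 6 h | – |
| Drugs withheld | dopaminergic PD drugs | PD drugs | – |
| Upper limit or target interval | none | none | none |
| Same interval at each visit | not required | not required | not required |
| Clock time of last PD dose at the exam | not required | not required | 6.3.5 and 6.3.6 ask for the usual dosing schedule; the Appendix C log has no such column |
| Use in the analysis | – | – | none in 9.4 |

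Video recording addresses the rater, not the interval. The timing of Day 1 is also loose. Footnote c places baseline assessments before randomization, while 6.2.1 allows other assessments during the 3-hour wait after the first dose.

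**Step 2: possible size.** The plan has no figure to reproduce: section 9.2 bases the sample size on funding and resources. Only the 10 per arm comes from the documents. All of the following are assumptions:

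- full PD-drug effect on Part 3, D = 8 or 12 points;
- exponential decay with half-life h = 3, 6 or 12 hours;
- intervals uniform on 6 to 14 hours and independent between visits;
- SD of change without drift, 4 or 6 points.

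Share of effect left at t hours: R(t) = 2^(−t/h). 
Shift between a 6-hour and a 14-hour exam: D × [R(6) − R(14)]. 
Moments over the interval: E[R^k] = [2^(−6k/h) − 2^(−14k/h)] / (8k ln2 / h). 
SD added to a change score: D × √(2 Var R).

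For h = 6 and D = 12:

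- Shift = 12 × (0.500 − 0.198) = 3.6 points.
- E[R] = 0.3016/0.9242 = 0.3263 and E[R²] = 0.2106/1.8484 = 0.11395.
- Var R = 0.11395 − 0.10648 = 0.00747.
- Added SD = 12 × √0.01495 = 1.47.

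| h | R(6) | R(14) | Shift, D = 8 / 12 | Added SD, D = 8 / 12 |
|---|---|---|---|---|
| 3 | 0.25 | 0.04 | 1.7 / 2.5 | 0.67 / 1.00 |
| 6 | 0.50 | 0.20 | 2.4 / 3.6 | 0.98 / 1.47 |
| 12 | 0.71 | 0.45 | 2.1 / 3.1 | 0.85 / 1.28 |

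Variance inflation = 1 + (added SD)²/SD².

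- Lowest: 1 + 0.67²/6² = 1.012.
- Highest: 1 + 1.47²/4² = 1.135 (1.1345 before rounding the added SD).

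The range is about 1% to 13%.

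**Step 3: wider half-lives.** At h = 1.5 the shift is 0.5 to 0.7 points, because little effect is left at 6 hours. At h = 24 it is 1.4 to 2.1 points, because the effect hardly changes between 6 and 14 hours. Both are smaller than at h = 6.

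**Step 4: the 10 versus 10 comparison.** With a t-test, two-sided 0.05 and 80% power, the detectable difference is 1.32 SD. The worst case multiplies the SD by √1.1345 = 1.065, giving 1.41 times the drift-free SD. Drift alone gives a chance between-arm difference with standard error 0.67 × √(2/10) = 0.3 to 1.47 × √(2/10) = 0.7 points.

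**The case against.** The strongest reply is that the effect is small and falls on the least important outcomes. Allocation is randomised 1:1, placebo is matched, and the PD regimen must be stable before baseline. A constant difference between drugs largely cancels in within-person change. Drift unrelated to arm is noise, and nothing in the documents suggests that it would follow the arm. A rise in SD of about 6.5% at worst matters little in a pilot sized on funding. All of this stands, and it limits the point to a cheap improvement.

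The reply is also right about three stronger readings that a reader might infer.

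- **That the scores do mix medicated and unmedicated states, or that 6 hours is too short for slow-release and patch products.** The documents give no duration of effect for any PD drug and no count of users. Appendix C is a template covering drugs ever taken, so a name on it does not show current use. The rule permits mixing but does not establish it. Nor do the documents supply a definition of the practically defined OFF state against which to fault 6 hours.
- **That nothing useful is recorded.** Sections 6.3.5 and 6.3.6 collect dosage, form, route and schedule, and medication is reviewed at Day 1 and weeks 2, 6 and 12. What the text does not require is the clock time of the last dose. The motor assessment form itself is not in the documents.
- **That Part 3 carries the efficacy claim.** That label is attached only to the TMS slope, which is also exploratory.

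None of this answers the core: the two definitions differ, the interval is free to vary, and the text gives no means of checking it.

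**Conclusion.** The point holds as a minor one about measurement and documentation. The OFF definition is an open-ended minimum, worded differently in two places, with no provision for a consistent or recorded interval. The likely consequence is avoidable noise in the exploratory Part 3 and TMS (OFF) change and slope: about 1% to 13% more variance if D is 8 to 12 points, h is 3 to 12 hours, intervals span 6 to 14 hours and the SD of change is 4 to 6 points. Every one of those inputs is assumed. Shorter half-lives, or intervals that in practice barely vary, would make the effect negligible.

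A reader might go further and infer a biased treatment comparison, or motor scores known not to be OFF scores. The documents support neither. What they support is that residual drug effect can be neither excluded nor examined afterwards. The primary safety and tolerability outcomes do not depend on this exam.

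**What to change.** 1. Reconcile footnote b of section 6.1 with section 6.3.8 on which drugs are withheld. Have the sponsor and clinicians state how the rule applies to slow-release and patch products. The withholding period is theirs to settle and is not proposed here.
2. Record the product and clock time of the last PD dose at every MDS-UPDRS motor assessment.
3. Book each participant's later exams at the same interval since the last dose, and the same time of day, as their own Day 1 exam. Fix where that exam falls on Day 1 by reconciling footnote c with section 6.2.1.
4. Report the interval by arm and visit. Add at most one sensitivity mixed model for Part 3 and TMS that includes hours since the last dose. I would not put that covariate in the main model, exclude users of long-acting products or rename the outcome: with 10 per arm, each is open to argument.

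The cost is one form field, a line of reporting and slightly less freedom in scheduling visits. No new procedure or staff is needed.

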6.2 Timing of Study Activities

6.2.1 Screening/Pre-Randomization Evaluations/procedures

Individuals identified at each site to potentially be eligible for inclusion will first be informed about the study and asked if they wish to receive more information. If the subject answers in the affirmative, approved staff will first go through the informed consent document with the subject and answer any questions that the subject may have. Specifically, the participant will be informed that signing this informed consent document does not guarantee that they will be included in the study. It simply allows the study sites to perform the necessary screening procedures to determine if the participant is eligible for randomization. If the participant signs the informed consent document, the participant will then be screened. This will include the following assessments:

- Review of inclusion/exclusion criteria
- Documentation of PD
- Hoehn & Yahr
- Review of concomitant medications/prohibited medications
- Orthostatics
- Medical history
- A physical exam
- Neurological exam
- Body weight and height
- Vital signs
- MDS-UPDRS Motor assessment
- Beck Depression Inventory, Beck Anxiety Inventory, Columbia-Suicide Severity Rating Scale

If the participant is found to be eligible for randomization based on this screening visit, their first baseline visit will be scheduled. The baseline visit must be scheduled within 90 days of the initial screening visit. If the participant is unable to schedule their baseline visit within 90 days of the screening visit, they may still be eligible for inclusion, but they will need to be re-screened.

After all assessments are completed, the site investigator will review the available data and ensure that the participant is eligible for randomization. If so, the participant will be randomized at Day 1. They will then be dispensed their study treatment packs. The participants will then have their blood drawn and then have their MRI. Immediately following this initial MRI, they will take their first dose of TZ 1mg or placebo. They will then wait 3 hours from that time, during which the other study assessments may be completed. After three hours from the time that they took their TZ, they will have their blood drawn again, and will then undergo another MRI study.

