6.2.2 On-Study/On-Interventions Evaluations/procedures

At each study visit, subjects will undergo the following assessments:

- Hoehn & Yahr
- Concomitant medication review
- Orthostatics
- Height and weight
- Vital signs
- Physical examination
- Neurological examination
- MDS-UPDRS Motor Assessment
- Cognitive Assessments
- Behavioral Assessments
- Sleep Assessments
- Fall Assessments
- Speech Assessments
- Motor Assessments

- Blood Draw
- Drug accountability/compliance
- Adverse Event Review

The likelihood of adverse events is highest near the initiation of study drug or at the time of dose escalation³⁴. Therefore, subjects will be contacted via telephone the following 3 weeks (weeks 3, 4 & 5) after starting study drug and after the 2 week visit. They will then be seen halfway through the study at 6 weeks. They will again be contacted 9 weeks after their baseline visit via telephone by the research coordinator, and their final visit will be 12 weeks after their baseline visit.

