9.1.2 Secondary Outcome(s)

- Mean change in systolic and diastolic blood pressure from baseline to 6 weeks and 12 weeks
- Prevalence of falls between placebo and active group
- Prevalence of intolerable side effects between placebo and active group
- Prevalence of study discontinuation between placebo and active group
- Differences in overall compliance between placebo and active group

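### Section 6.2.1 permits Day 1 assessments after the first capsule, contrary to footnote c, so a site could take the blood pressure baseline post-dose

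*Combined protocol and SAP*

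**What the plan says.** The schedule in Section 6.1 marks orthostatics and vital signs on Day 1, together with motor, behavioral, sleep, cognitive, speech and mobility assessments. Footnote c to that schedule reads: "Baseline assessments on day 1 will occur PRIOR to randomization or the study drug being dispensed".

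Section 6.2.1 gives its own sequence. It starts with an eligibility check: "After all assessments are completed, the site investigator will review the available data and ensure that the participant is eligible for randomization". Randomization on Day 1 follows. Next: "They will then be dispensed their study treatment packs. The participants will then have their blood drawn and then have their MRI". Straight after that scan, "they will take their first dose of TZ 1mg or placebo". Then comes the sentence at issue: "They will then wait 3 hours from that time, during which the other study assessments may be completed". A second blood draw and a second MRI close the visit.

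The outcome that depends on the Day 1 reading is in Section 9.1.2: "Mean change in systolic and diastolic blood pressure from baseline to 6 weeks and 12 weeks". That section does not say which reading is the baseline. An earlier reading is taken at screening, and on timing Section 6.2.1 says: "The baseline visit must be scheduled within 90 days of the initial screening visit".

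**The concern.** The two instructions cannot both be followed in full. Under footnote c every Day 1 baseline assessment is finished before the drug is handed over. Under Section 6.2.1 some assessments may be done while the first dose is taking effect, and the text neither names them nor rules any out.

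Blood pressure is the measure for which this matters most. TZ is an alpha-1 antagonist, and the stated reason for the secondary objective is that it could worsen orthostatic hypotension. If the Day 1 reading in a TZ participant is taken after the capsule, any acute fall is already in the baseline and drops out of the change to weeks 6 and 12. Placebo participants have no drug effect to offset it. The error therefore runs one way, toward no TZ effect, in a study whose main purpose is safety. It enters both follow-up times and would not shrink with more participants.

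**Working it through.** **Step 1. Does the conflict exist?** Side by side:

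| Day 1 item | Footnote c, Section 6.1 | Section 6.2.1 |
|---|---|---|
| First blood draw and MRI | Before randomization or dispensing, if counted as baseline assessments | After dispensing, before the capsule |
| Vital signs, orthostatics, other Day 1 assessments | Before randomization or dispensing | Not placed individually; the remaining assessments may be done in the 3 h after the capsule |

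Falls, drug accountability and adverse event review carry no Day 1 mark. If footnote c were followed in full, no scheduled assessment would remain for the 3 h wait. The permission has an effect only if some Day 1 assessments are done post-dose, so it is a real conflict.

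**Step 2. Direction and size.** The documents give no acute blood pressure effect, no SD and no power calculation, so there is no figure of the plan's own to reproduce. Let:

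- n = 10 per arm (protocol synopsis, sample size);
- k = number of TZ participants whose Day 1 reading is post-dose (unknown);
- d = fall caused by TZ 1 mg at the time of that reading (unknown; assumed 2, 5 or 10 mmHg).

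The mean TZ baseline is lowered by d × k/10. Change is follow-up minus baseline, so the TZ change becomes

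(follow-up − (baseline − d × k/10)) = (follow-up − baseline) + d × k/10.

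The placebo change has no such term. The between-arm difference in change therefore moves toward zero by d × k/10:

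| Assumed d (mmHg) | k = 1 | k = 5 | k = 10 |
|---|---|---|---|
| 2 | 0.2 | 1.0 | 2.0 |
| 5 | 0.5 | 2.5 | 5.0 |
| 10 | 1.0 | 5.0 | 10.0 |

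**Step 3. Against the precision of the trial.** The 95% half-width for a difference of two means is t(0.975, 18 df) × SD × sqrt(2/10), with t = 2.101 and an assumed SD of change:

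- SD 10: 2.101 × 10 × 0.4472 = 9.4 mmHg;
- SD 15: 2.101 × 15 × 0.4472 = 14.1 mmHg.

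With d = 5, one affected participant (0.5 mmHg) is 0.5/9.4 = 5% of the half-width at SD 10 and 0.5/14.1 = 4% at SD 15. Half the arm (2.5 mmHg) is 27% or 18%, and the whole arm (5 mmHg) is 53% or 35%. The last two cases need half or all of the TZ arm to be measured contrary to footnote c.

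**Step 4. After the fix.** With every Day 1 reading pre-capsule, k = 0 and this bias is 0 mmHg. The sample size does not change.

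**The case against.** The strongest reply is that pre-dose blood pressure is already the likely practice. Footnote c is explicit. Section 6.2.1 itself puts randomization after completed assessments. The eligibility review is marked on Day 1, Section 4.2 has an exclusion defined by a postural fall in blood pressure, and Section 4.5 allows no eligibility waivers. Orthostatics therefore feed a decision made before randomization. On this reading the 3 h permission covers tests with no eligibility role, such as cognition, sleep, speech and finger tapping. Drawing blood and scanning after dispensing does no harm, because both still precede the capsule.

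Most of this stands, and it is why the point is put as something a site could do. It does not close the gap. The sentence about completed assessments follows the screening paragraphs and does not say whether Day 1 is meant. The postural exclusion can be checked on the screening orthostatics. And if the permission was meant only for non-eligibility tests, the text does not say so; some of those tests also serve as baselines for the exploratory slopes.

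It is also fair that baseline reasonably means Day 1, since footnote c uses that word and Section 6.2.1 separates the baseline visit from screening. What is missing is a statement that the value is the pre-capsule one. The screening reading is certainly pre-drug and could support a sensitivity check, but it may be up to 90 days older.

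Three stronger inferences are tempting and not supported:

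- *That the blood pressure result will be materially biased.* The acute fall after 1 mg, the SD and the share affected are all assumed. The statement in Section 6.2.2, "The likelihood of adverse events is highest near the initiation of study drug or at the time of dose escalation", justifies the telephone calls; it says nothing about blood pressure within 3 h of 1 mg.
- *That the safety conclusions as a whole are affected.* Drop-out, adverse events, falls and the prevalence of orthostatic hypotension in Section 9.4 do not use change from baseline.
- *That unrecorded time since dose undermines the readings at weeks 2, 6 and 12.* Section 5.1 already fixes bedtime dosing at least 23 h apart, the randomized comparison remains valid for the time measured, and the visit forms are not in the documents, so missing time fields cannot be shown.

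**Conclusion.** The conflict between Section 6.2.1 and footnote c is real, and as written it allows a post-dose blood pressure baseline. A pre-dose reading remains the more likely practice. If some TZ participants were read post-dose, the measured change to weeks 6 and 12 would be understated by the acute effect times the share affected. The size cannot be taken from the documents. The illustration of 0.5 mmHg per affected TZ participant assumes an acute fall of 5 mmHg and 10 per arm; the multi-mmHg figures also assume that half or more of the arm is affected. The reach is limited to change-from-baseline measures, chiefly the blood pressure outcome. This is a small ambiguity with a one-directional consequence for a safety outcome. It is worth correcting because the correction is nearly free.

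**What to change.** Amend Section 6.2.1 so that Day 1 vital signs, orthostatics and all other assessments used as baselines are completed before the first capsule. Only the repeat blood draw and repeat MRI should follow it. If a post-dose blood pressure is wanted for safety, allow it as an extra reading, labelled separately and not used as baseline. In Section 9.1.2, state that the pre-capsule Day 1 value is the blood pressure baseline.

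The cost is one or two sentences and a longer pre-dose session on Day 1, since the 3 h wait can no longer absorb the assessments. As an optional extra, the site could note the time of the last dose at later visits; nothing in this point depends on it.
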